8.1 Statistical analysis of the primary endpoints

The primary analysis of this study is descriptive and no formal hypothesis testing will be conducted. For the primary analysis, adverse event rates will be calculated by dividing the number of reported safety events by the patient-years at risk. Cimzia-specific rates will be calculated and compared to all other CD treatment rates.

Propensity scores will be used to assess the comparability of patients who are receiving Cimzia at baseline to those who are receiving another CD medication. Appropriate analytical methodologies will be used to investigate the effect of time varying confounders.

Time-to-event analyses for each Adverse Event of Interest will be conducted using Cox proportional hazard modeling and Kaplan-Meier curves.

Analyses of specific outcomes may be conducted if appropriate.

8.1.1 Malignancy events

The following analyses will be conducted to better elucidate treatment patterns and treatment attribution in malignancy events:

- The number of malignancy events and number of patients experiencing malignancy events will be tabulated by the number of CD treatments received during the study up to and including the onset date of malignancy. Also, the mean number of treatments

received per patient in the Cimzia and comparator groups (based on baseline assignment) will be calculated, as well as for both groups combined.

- The number of malignancy events and number of patients experiencing malignancy events will be tabulated by treatment patterns for biologics observed in the study. The name and order of the biologic treatment will be specified in the summary table (eg, “A-B” implies that patients received two different biologics, “A” followed by “B”; “C” implies that patients received biologic “C” throughout the study; “A-C-D” implies that patients received three different biologics, in the order of “A”, “C”, then “D”, etc.).
- The number of malignancy events and the number of patients experiencing malignancy events will be tabulated by the type of CD therapy received (monotherapy versus combination therapy). If a patient received combination therapy (TNF- α antagonist plus immunosuppressant) at least once during the study, then this patient will be included in the combination therapy category.

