8.2.1 Extent of exposure

Length of exposure (weeks), length of exposure category (weeks) and total years of exposure will be presented. This summary will be repeated for each of the exposure definitions presented in Section 3.2.1.

In order to summarize treatments received by both cohorts (ie, treatment switch patterns), descriptive statistics by cohort will be presented for the number of events, the number of exposure patients, and for person-time calculations.

A stratified analysis by cumulative Cimzia exposure may also be performed for malignancy events to identify potential patterns in long-term use of Cimzia.

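### SAP 8.1.1 specifies its three malignancy tables as counts without patients at risk or person-years per category, and two of them let treatment after diagnosis set the category

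*SAP*

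**What the plan says.** SAP 8.1.1 introduces the three tables as a means "to better elucidate treatment patterns and treatment attribution in malignancy events". Each is specified as the number of malignancy events and the number of patients who had them.

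- **Number of treatments:** "tabulated by the number of CD treatments received during the study up to and including the onset date of malignancy". The section also asks for the mean number of treatments "received per patient in the Cimzia and comparator groups (based on baseline assignment) will be calculated". This is the only figure in 8.1.1 that covers all patients.
- **Biologic sequence:** both counts are "tabulated by treatment patterns for biologics observed in the study".
- **Monotherapy or combination:** a patient goes into the combination category on this condition: "If a patient received combination therapy (TNF- α antagonist plus immunosuppressant) at least once during the study".

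Protocol 6.4.1.1 lists the same three tables. There the number-of-treatments table has no cut at onset either; the SAP added the cut to that table alone.

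On denominators, SAP 8.2.1 has switching between treatments in view and promises this: "descriptive statistics by cohort will be presented for the number of events, the number of exposure patients, and for person-time calculations". SAP 3.6 sorts malignancy person-time into two groups, Cimzia and Comparator. SAP 8.1 and 8.1.4 give rates per patient-years for that comparison.

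**The concern.** Malignancy is the primary outcome. Under SAP 3.2.1.1, any malignancy after a first Cimzia dose is assigned to Cimzia, whatever was taken later. Readers will naturally turn to the 8.1.1 tables to ask whether a sequence of biologics, or combination therapy, accounts for some of those cancers.

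A count cannot answer that. A category can hold most of the cancers because most of the follow-up lies in it, or hold few and still carry a raised rate. The problem is compounded where the category is fixed from the whole study, because a change of treatment made after the diagnosis can then move the cancer from one row to another.

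**Working it through.** The plan gives no figure to reproduce here, so the check has two parts: what the text supplies, and how far counts alone can mislead. All event counts, person-time shares, hazards and switch rates below are assumptions.

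**1. Where a denominator per category might come from**

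| Source | What it gives | Covers the three classifications? |
|---|---|---|
| SAP 8.1.1 | Events, patients with events, mean number of treatments by baseline group | No |
| SAP 8.2.1 | Events, exposed patients and person-time, by cohort | Not stated |
| SAP 3.6, 8.1, 8.1.4 | Malignancy person-time and rates, Cimzia v Comparator | No |
| SAP Table 8.1 with 3.6 | Malignancies also under acute rules: Cimzia, Comparator, Overlap, Gap | No; see the objection |
| SAP 8.2.1, optional | Malignancy by cumulative Cimzia exposure | No |
| SAP 3.1 | Rule for the denominator of percentages | No; 8.1.1 asks for numbers, not percentages |

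**2. Share of events against share of person-time**

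If combination therapy holds a share s of person-time and multiplies the rate by RR, its share of events is s·RR / (s·RR + 1 − s).

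- s = 0.4, RR = 1.5: 0.60/1.20 = 0.50
- s = 0.3, RR = 1.5: 0.45/1.15 = 0.39
- s = 0.2, RR = 2: 0.40/1.20 = 0.33

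In the first case the counts are equal. In the other two, combination shows fewer cancers than monotherapy although its rate is higher.

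**3. The same counts with different denominators**

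Person-years for scale come from SAP 2.4 (3045 patients, 8 years, 8% annual drop-out): 3045 × (1 − 0.92^8) / (−ln 0.92) = 17,777, taken as 17,800. Assume 20 malignancies on combination and 40 on monotherapy. The standard error of the log rate ratio is √(1/20 + 1/40) = 0.274.

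| Combination share of person-time | Rate per 100 PY, combination | Rate per 100 PY, monotherapy | Rate ratio (95% CI) |
|---|---|---|---|
| 20% | 20/3,560 = 0.562 | 40/14,240 = 0.281 | 2.0 (1.17 to 3.42) |
| 33.3% | 0.337 | 0.337 | 1.0 (0.58 to 1.71) |
| 50% | 20/8,900 = 0.225 | 40/8,900 = 0.449 | 0.5 (0.29 to 0.86) |

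**4. Would patient totals be enough?**

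A simulation with no treatment effect (200 studies of 3045 patients) used a constant hazard of 0.5 per 100 PY, 0.25 switches per year, 8% annual drop-out and 8 years. Treatments were counted to malignancy or end of follow-up.

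| Treatments | Expected events | Patients | Patients with an event |
|---|---|---|---|
| 1 | 42 | 947 | 4.4% |
| 2 | 25 | 850 | 3.0% |
| 3 | 12 | 626 | 2.0% |
| 4 | 5 | 363 | 1.4% |

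The hazard is the same throughout, yet both the counts and the percentages fall steeply. Cases stop collecting treatments at onset while other patients go on. Only person-years by current number of treatments return the true rate, which is 0.5 per 100 PY in every row by construction.

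**5. The cut at onset**

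Take a patient on an anti-TNF alone who develops a malignancy and later receives an immunosuppressant with an anti-TNF. Under 8.1.1 the cancer is counted under combination. If person-years were split by current category but this numerator rule stayed, the cancer would sit in the combination numerator and the time leading to it in the monotherapy denominator. The sequence table has the same weakness, since a biologic started after diagnosis lengthens the sequence.

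**The case against.** The strongest reply is that the tables are case descriptions. Their stated purpose concerns patterns and attribution in malignancy events, all analyses are descriptive, and the comparison that matters already has person-time. That is fair, and it means the tables do have a use: they show what had been taken by patients whose cancers the ever-exposed rule assigns to Cimzia.

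A second reply is that attribution is examined elsewhere. SAP Table 8.1 states that malignancies are also analysed under acute rules, which split events and person-time by treatment at onset. This stands, but it does not replace the 8.1.1 tables. Overlap there means Cimzia with any comparator class, corticosteroids included, while another anti-TNF plus an immunosuppressant falls within Comparator. Biologic order and number of treatments do not appear. Rate ratios against other treatments or classes (SAP 8.1.5) are only to be done as appropriate.

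A third reply is that 8.2.1 is aimed at switch patterns, and that 'by cohort' might mean cohort columns within pattern rows. The table shells mentioned in SAP 12.1 might show this, but they are not part of the documents. The wording is open enough that missing denominators in the final tables cannot be asserted. What can be said is that the SAP text does not require them.

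**Conclusion.** As specified, the three tables describe what cases received but cannot show whether malignancy is more frequent under a given number of treatments, biologic sequence or combination therapy. Two of the three can also place a cancer by treatment given after it was diagnosed. The size in this registry is unknown. Under the assumed counts, the same table fits a doubling, no difference or a halving of the rate as the combination share of person-time runs from 20% to 50%.

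Three stronger conclusions are tempting and do not follow:

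- That the tables say nothing about attribution. They do describe the treatment history of the cases.
- That they are the SAP's only look at treatment history behind malignancies. The acute-rule analysis is another, with person-time.
- That the primary malignancy comparison lacks a denominator. It has patient-years and, for incidence rates, Poisson intervals.

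The point therefore leaves the Cimzia versus Comparator rates untouched. It is worth correcting because the outcome is primary and the tables invite comparison across rows.

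**What to change.** In each 8.1.1 table, classify both the malignancies and the person-time by the time-updated category, that is, by the treatments received up to that moment and, for a case, up to and including onset. For each category show:

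- patients who entered it;
- patients with a first malignancy while in it;
- person-years accrued in it up to first malignancy or end of follow-up;
- the incidence rate per 100 patient-years with the Poisson interval of SAP 8.1.4.

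Keep the count of all malignancy events as a separate column. It should not be divided by person-time that stops at the first malignancy.

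Adding person-years to the tables as they stand would not be enough, because the sequence and combination numerators would still be classified over the whole study.

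The cost is a time-varying derivation of each classification from the dosing data already held for the acute rules. This is more than an extra column, since malignancy person-time is now derived for two groups only. Rare sequences will have sparse cells and wide intervals, and may need pooling.

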4.7 Participation and Retention Strategies

Individual patient follow-up is approximately 8 years after enrollment, regardless of discontinuation of Cimzia or other medications.

As a means to retain patient participation, patients are followed up directly via a web-based system or if preferred, by mail (including a prepaid self-addressed return envelope) or by the phone every 3 months throughout the study (unless the patient withdraws consent or is deemed lost to follow-up) to complete a patient survey. “Lost to follow-up” is defined as a patient who goes 2 years with no data being collected/reported (2 years without Investigator visit/telephone contact or failure to at least partially complete 8 consecutive quarterly patient surveys; further attempts at patient contact are not required). The patients will receive emails or postal mail reminding them to complete the survey. If they have not completed the survey one week after the due date, they will be called by the independent patient interview service to complete the survey via phone. Patients completing the quarterly surveys will receive a nominal appreciation gift (if approved by the site’s IRB).

In the event an Investigator retires, or discontinues participation from the registry, the following transition plan is in place to enable continuing participation of their patients. The Informed Consent Form include wording explaining that if the patient’s Investigator discontinues participation in the registry, or retires, the independent patient interview service will be notified and the name and contact information of the closest participating study Investigator that they can contact during the remainder of their participation in the registry. The new Investigator and the patient should document re-consent of the transition. The registry can continue to collect the direct patient-reported data without the need for re-consent. If the patient is unable or unwilling to be followed by a new Investigator, the patient must be discontinued from the study.

In the event a patient moves to a new location or chooses to leave their current Investigator, patients are provided with information upon enrollment as to how to locate a participating Investigator in their area or how to provide the registry information to a new Investigator that may not yet be participating. Participating patients will have access to all of this information on the study specific web portal.

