6.4.1.1 Malignancy Events

The following analyses will be conducted to better elucidate treatment patterns and treatment attribution in malignancy events:

- The number of malignancy events and number of patients experiencing malignancy events will be tabulated by the number of CD treatments received during the study. Also, the mean number of treatments received per patient in the Cimzia and comparator groups (based on baseline assignment) will be calculated, as well as for both groups combined.
- The number of malignancy events and number of patients experiencing malignancy events will be tabulated by treatment patterns for biologics observed in the study. The

[figure not shown]
name and order of the biologic treatment will be specified in the summary table (eg, “A-B” implies that patients received two different biologics, “A” followed by “B”; “C” implies that patients received one biologic “C” throughout the study; “A-C-D” implies that patients received three different biologics, in the order of “A”, “C”, then “D”, etc.).

- The number of malignancy events and the number of patients experiencing malignancy events will be tabulated by the type of CD therapy received (monotherapy versus combination therapy). If a patient received combination therapy (TNF- α antagonist plus immunosuppressant) at least once during the study, then this patient will be included in the combination therapy category.

Due to the long latency of malignancy, gaps in exposure will not be factored into person-time calculations for malignancies. Any patient exposed to Cimzia during the study will only contribute person time to the Cimzia cohort from that point onward **Figure 6–1**.

As an example, if a malignancy should occur any time after Cimzia exposure, it will be attributed to Cimzia. If a malignancy occurred in a patient prior to Cimzia exposure or in a patient with no Cimzia exposure, then it would be attributed to comparator. Thus, a patient may have exposure to multiple biologics, but any malignancies diagnosed after treatment with Cimzia would be systematically attributed to Cimzia.

Figure 6–1: Example person-time at risk for malignancy events

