3.2.1.1 Person-time at risk calculations for malignancy

Due to the long latency of malignancy, gaps in exposure between treatments will be attributed to the most recent, previous treatment. Gaps in exposure before first known treatment will not be factored into person-time calculations for these events. Any patient exposed to Cimzia during the study will only contribute person-time to the Cimzia cohort from that point onward (Figure 1). As an example, if a malignancy should occur any time after Cimzia exposure (including when Cimzia was known to be used prior to enrollment), it will be attributed to Cimzia. If a malignancy occurred in a patient prior to Cimzia exposure or in a patient with no Cimzia exposure, then it would be attributed to comparator. Thus, a patient may have exposure to multiple comparator drugs, but any malignancies diagnosed after treatment with Cimzia would be systematically attributed to Cimzia, even after ending or switching from Cimzia.

Figure 1: Example person-time at risk for malignancy events

Exposure person-time at risk will be calculated for each CD treatment using the following equation:

$$\text{Last Date} - \text{First Date} + 1$$

where all person-time is contributed to Cimzia after first Cimzia dose is administered.

First date is defined as the latest enrollment date or first CD treatment date after enrollment (whichever is later) or first Cimzia dose date if switching from a comparator treatment after enrollment. Last date is defined as the earliest of the following:

- Date of safety event of interest (for incidence rate calculations only)

- Date of discontinuation, withdrawal, or data cutoff

See Section 11.1, appendix 1 for more examples of treatment allocation scenarios for malignancies.

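### Two of the three malignancy tables in SAP 8.1.1 let treatment begun after the cancer decide how the case is classified

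*SAP*

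**What the plan says.** SAP 8.1.1 introduces three tabulations of malignancy events and of patients with malignancy, intended "to better elucidate treatment patterns and treatment attribution in malignancy events". Their time windows differ:

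- **Bullet 1, number of treatments.** Events and patients are "tabulated by the number of CD treatments received during the study up to and including the onset date of malignancy".
- **Bullet 2, order of biologics.** Events and patients are "tabulated by treatment patterns for biologics observed in the study". The worked example of a single biologic also refers to the whole study.
- **Bullet 3, monotherapy or combination.** A patient who received a TNF antagonist plus an immunosuppressant "at least once during the study, then this patient will be included in the combination therapy category".

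Protocol 6.4.1.1 has the same three bullets, none limited to onset. Its first bullet reads "tabulated by the number of CD treatments received during the study. Also", the last word opening the next sentence. The SAP therefore added the limit to bullet 1 and left the other two essentially as they were.

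**The concern.** Treatment begun after a cancer cannot have contributed to it. If a patient is diagnosed on monotherapy and first receives combination therapy two years later, bullet 3 counts the cancer under combination therapy. If a patient is diagnosed on biologic A and later moves to B, bullet 2 counts it under the sequence A-B. Bullet 1 would use only what came before onset, so adjacent tables would describe the same case on different terms.

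Malignancy is the primary outcome, and these tables are where a reader would look for a link with combination therapy or with a particular sequence of biologics. What is at stake is whether their rows can be read as exposure before the cancer.

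**Working it through.** **1. Is there a limit elsewhere?** The only cut at the event date is in the person-time rule of SAP 3.2.1.1: "Date of safety event of interest (for incidence rate calculations only". That governs denominators for incidence rates. Sections 3.6, 8.1.3 and 8.1.4 and Appendix 1 deal with Cimzia, comparator, gap and overlap. None of them governs biologic sequence or combination status. Tables with an onset limit: 0 of 3 in the protocol, 1 of 3 in the SAP.

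**2. Can treatment after onset be in the data?** Yes. Protocol 4.7 states: "Individual patient follow-up is approximately 8 years after enrollment, regardless of discontinuation of Cimzia or other medications". Malignancy is not given as a reason to leave the registry. Appendix 1 itself lists patients treated after a cancer.

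**3. Do the rules collide?** Each scenario below has no Cimzia before consent. In each, Appendix 1 assigns the malignancy (in 15a, the first) to comparator, with no malignancy time on Cimzia.

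| Scenario | Treatment in study | Malignancy | Bullet 2 read literally |
|---|---|---|---|
| 3a | Comparator, Cimzia, comparator | First comparator period | A sequence containing Cimzia |
| 14a | Comparator, gap, Cimzia | Gap | A sequence containing Cimzia |
| 15a | Comparator, gap, Cimzia | First in gap, second on Cimzia | A sequence containing Cimzia, for both events |
| 16a | Gap, Cimzia | Gap | Cimzia as the only biologic |

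The same cancer is a comparator event in the rates and sits in a Cimzia row of the pattern table. For the second event in 15a, the Cimzia row is consistent with treatment before that event.

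**4. How large could it be?** The plan states no figure to reproduce and no rate of starting combination therapy. The following illustrates bullet 3 only. Assumptions: constant yearly hazard h of first combination therapy, share p0 already on it at entry, onset uniform over F = 8 years, follow-up to year 8.

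- On combination by onset: pre = p0 + (1 − p0)[1 − (1 − e^(−hF))/(hF)]
- Ever on combination: ever = p0 + (1 − p0)(1 − e^(−hF))
- Share of the combination row that is there only through later treatment: (ever − pre)/ever

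For h = 0.05 and p0 = 0: e^(−0.4) = 0.670, so pre = 1 − 0.330/0.4 = 0.176, ever = 0.330, and the share is 0.154/0.330 = 46.7%.

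| p0 | h | pre | ever | share |
|---|---|---|---|---|
| 0 | 0.02 | 0.076 | 0.148 | 48.7% |
| 0 | 0.05 | 0.176 | 0.330 | 46.7% |
| 0 | 0.10 | 0.312 | 0.551 | 43.4% |
| 20% | 0.02 | 0.261 | 0.318 | 18.1% |
| 20% | 0.05 | 0.341 | 0.464 | 26.5% |
| 20% | 0.10 | 0.449 | 0.641 | 29.9% |

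This takes the hazard as unchanged by the cancer. Now let it become r = k·h after onset, and apply the plan's 8% annual drop-out after onset, d = −ln 0.92 = 0.083 per year. Then post = (1 − p0) × mean over onset t of e^(−ht) · [r/(r + d)] · [1 − e^(−(r + d)(8 − t))], and the share is post/(pre + post). With h = 0.05 (shares from unrounded values):

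| k | share, p0 = 0 | share, p0 = 20% |
|---|---|---|
| 1 | 41.7% | 22.8% |
| 0.5 | 27.5% | 13.5% |
| 0.25 | 16.3% | 7.5% |
| 0 | 0% | 0% |

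The answer runs from 0% to 49% depending only on assumed inputs. It shows that the rule can matter. It does not estimate how much.

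**The case against.** The strongest reply is that these are two supplementary count tables, without denominators, in a study declared descriptive (SAP 2.1.1 and 8.1). The attribution that drives the results is handled correctly elsewhere: SAP 3.2.1.1, 3.6 and 8.1.3 assign a malignancy by Cimzia exposure before the event, and Appendix 1 shows that later Cimzia does not relabel an earlier cancer. That stands. A reader might infer from the inconsistency that the primary malignancy comparison is biased. It is not, because the rates and hazard ratios do not use the 8.1.1 categories.

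A reader might also infer that every case is misfiled, or that anyone whose regimen changes after diagnosis is, say 10–20% of cases. The text does not support this. Stopping a drug, or stepping down from combination to monotherapy, moves nobody in either table. A change of immunosuppressant or steroid alone does not alter a biologic sequence. Only additions count, and any such percentage would have no source in the documents. If treatment after cancer is mostly reduced, the error is small.

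Bullet 2 is the weaker case. The stated aim covers patterns as well as attribution, and a whole-study sequence is a legitimate description of patterns. This stands in part: the table is at fault only when read for attribution, and nothing in 8.1.1 warns against that reading.

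Two further replies carry less weight. The bullets follow protocol text added in Amendment 4, when the statistical section was updated after FDA comments on switching. But SAP bullet 1 already departs from that text in the direction proposed. The listings of adverse events and CD medication history should let someone with access reconstruct the order of treatment and onset, but that does not correct the tables.

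**Conclusion.** The point holds as a narrow error in a stated rule. Bullet 3 explicitly allows treatment after onset to define the case. For bullet 2 this follows from the whole-study wording and the absence of the limit that bullet 1 carries. Both tables can therefore contradict bullet 1 and the comparator rule in SAP 3.2.1.1. Descriptive status is no defence here, since description is all that these tables offer.

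Only patients who add a biologic, or first start combination therapy, after onset change cell. How many do so is unknown from the documents, and it could be close to none. It is worth correcting because the remedy is simple, but no main result depends on it.

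**What to change.** In SAP 8.1.1, add to bullets 2 and 3 the limit that bullet 1 already has, "up to and including the onset date of malignancy". Say which onset governs when a patient has more than one malignancy, since scenarios 15a and 15b foresee this: each event's own onset for event counts, the first onset for patient counts. Provide a row in the sequence table for cases with no biologic in the study by onset, such as 16a.

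If the whole-study sequence is wanted, keep it as a separate table labelled as describing treatment patterns only.

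The cost is a short text change and minor programming. Treatment and onset dates are already needed for bullet 1 and for the Appendix 1 allocation, so no new data are required. Person-years per category would be a further analysis and is not needed to cure this defect.
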